We will recruit 280 participants; 70 in each of the four arms. Wiberg-Itzel et al [2] observed mean umbilical artery pH 7.23 (SD 0.07) in the non-intervention group. With our sample size, we will have 80% power (significance level 0.05) to detect mean pH changes of 0.04 and above in each arm. We are interested in detecting an effect size of 0.2 and above, which we deem to be a moderate effect size. The total sample size needed to detect a between-factor mean effect size of 0.2, by repeated measures analysis of variance (ANOVA) with a type 1 error margin of 5%, across 4 groups with 5 repeated measurements; was 224 at a power of 91%. Assuming a 20% loss to follow up in our study; we will need 280 participants (70 in each of the 4 groups). The sample size was calculated using G* Power software version 3.1 using the test family for the F test, and the statistical test for ANOVA repeated measures, between factor analysis & within-between interaction [10]. Therefore, our sample size will also be sufficient to detect a within and between-subject interaction (intervention and time interaction) with a power of 99%. To obtain these estimates, we will construct an interaction term between the intervention and the time variable. We are confident that we shall be able to accrue this number of participants in a period of six calendar months, on the basis of our experience working in the same hospital [7]. In order to detect a change in maternal pH, a minimum of two measurements are needed from a participant. However, with improvement of obstetric care, many women deliver within 30 minutes of taking the baseline measurements and hence no second measurement is obtained. To account for this form of right censoring, we have inflated our sample size by 192 participants to ensure that we have at least 280 women with at least two pH measurements. We will recruit 472 participants; 118 in each of the four arms.

Outcome variables

The primary outcome measure will be the mean change in maternal pH from baseline in each group. The secondary outcomes will include, mean pH and lactate in maternal and umbilical blood, early neonatal death, safety (side effects) of sodium bicarbonate, primary PPH, sepsis and death. Furthermore, the plasma concentrations of HCO₃ levels will be measured as well to accurately estimate the required dose.

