Randomisation: A sequence of random numbers will be generated by an independent biostatistician using an online randomization service at www.sealedenvelope.com in permuted block sizes of four, six and eight. An independent, off-site pharmacist will prepare and consecutively number identical study packages using

the generated random numbers. This will ensure that the allocation is concealed. At the study site, after gaining consent, the research midwife will take the next sequentially labeled study drug package and administer its contents to the eligible participant. Therefore, both the participants and data collectors will remain blinded throughout the study.

Intervention/ Comparator: Eligible participants will be randomly assigned to receive 100 mls (8.4g), 150 mls (12.6g) and 200 mls (16.8g) of 8.4% sodium bicarbonate solution, or placebo (50 mls of NS 0.9%) in a ratio of 1:1:1:1. The study drug (Sodium Bicarbonate 8.4% and Normal Saline 0.9%) will be contained in identical 25 mL glass vials (Neon Laboratories Ltd, Mumbai, India), administered intravenously as a single bolus dose. Since the average waiting time for CS in our labour ward is approximately 110 minutes [11], there will be no need for a repeat dose.

In addition, all patients will receive the available Ministry of Health recommended standard preoperative care for all patients with OL which includes antibiotic prophylaxis, intravenous fluid replacement (1.5 L of normal saline), bladder drainage and lying in left-lateral position as they are being prepared for caesarean section [23]. Details in flow diagram 1.

Data collection

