Data analysis plan

Data will be analyzed using Stata version 17.0 (StataCorp; College Station, TX, USA). We will describe categorical variables as proportions and compare them with chi-squared tests or Fischer's exact tests as appropriate. We will describe continuous variables as means (SD) OR medians (IQR) and compare them with t tests or Mann-Whitney U tests as appropriate. Our analysis will be by intention to treat. To determine the safety of sodium bicarbonate infusion, we will compare the incidence of side effects in each arm and report risk differences.

For the primary outcome of acidosis (pH and lactate) between-subjects repeated measures ANOVA will be conducted. We will also conduct within-subject interaction repeated measures ANOVA to assess for differences in the rate of change of pH between the groups.

We will use histograms, P-P plots, k-density, and Q-Q to assess the distribution of normality of continuous outcomes. In case the distribution of normality is not met; we shall transform our data and this decision will be guided by Stata's *gladder* command that shows various transformation options.

All analyses will be followed by a Bonferroni posthoc test for multiple comparisons, a Friedman test to compare rates of change between the various groups, and a Mauchly's test of Sphericity to check for equal variance among the combinations of the various groups. We will use Margins and Margins plots to obtain marginal means and graphical descriptions of the interaction between various groups and time.

Data Monitoring

Independent Data Monitoring Committee (IDMC)

An independent data monitoring committee (IDMC) will be appointed consisting of 3 members: a statistician, an obstetrician/gynaecologist, and a paediatrician. They will operate according to the IDMC charter, which will be developed with the members. IDMC will be encouraged to follow the recommendations of the international DAMOCLES group for IDMC activities.[12] The IDMC will monitor the trial once with a focus on issues relating to the quality of trial conduct, such as overall and site-specific rates of recruitment, adherence to trial interventions, visit schedules, losses to follow-up, and administrative and safety data. It will review administrative and safety data approximately every three months. The treatment groups will be masked in the IDMC reports.

Interim analyses and stopping guidelines

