short turnaround time on blood results to inform clinical decision making. In the event of system downtime, we will use a YSTE-BG100 Blood Gas Analyzer (Yuesen Med, China) as a backup. The YSTE-BG100 is a compact and user-friendly device that can rapidly assess key parameters including pH, lactate, glucose, electrolytes, and blood gases [17], thereby ensuring continuity of care even when the RAPIDPoint® 500e Blood Gas System is down. In our previous trial the study drug was sourced from the local supplier accredited by the National Drug Authority (NDA). We intend to use 8.4% sodium bicarbonate (intervention), and sodium chloride 0.9% (placebo) from NEON laboratories Ltd, Mumbai, India.

Adverse events/side effects: Based on the package insert labelling for sodium bicarbonate and a review of the literature [18], we will actively monitor for the following; increased thirst, continuing loss of appetite, swelling of the lower limbs, venous irritation, muscle pain or twitching, continuing headache, nausea or vomiting, stomach cramps, unusual tiredness or weakness, nervousness or restlessness, mood or mental changes, frequent urge to urinate, slow breathing and cellulitis at the injection site. This will be done hourly for the first six hours, six hourly for the next 18 hours and then daily throughout the period of hospitalization.

Follow-on plan

We plan to publish our results in a peer reviewed journal irrespective of the findings, as we have demonstrated in the past. Furthermore, we have established contact with [name] in Oslo to advise on the setup of our current study. His group is undertaking similar work (<https://ichgcp.net/clinical-trials-registry/NCT05719467>), and they could be potential collaborators on a larger grant application if the results are positive (see attached support letter). We have a community advisory group that is crucial in disseminating our findings to the lay public. [name] is also a member of National Safe Motherhood Executive Committee (NASMEC), a ministry of health technical advisory group on maternal health. He will disseminate the findings in this group.

Table 2: Proposed study timelines

Activity	2024												2025					
	Jan	Feb	Mar	Apr	May	Jun	Jul	Aug	Sep	Oct	Nov	Dec	Jan	Feb	Mar	Apr	May	Jun
REC & UNCST approvals	*	*	*	*	*													
Recruitment of staff					*	*	*											
Procurements		*	*	*	*	*	*	*	*	*	*							
Data collection							*	*	*	*	*	*	*	*	*	*	*	*
Data analysis											*	*	*	*	*	*	*	*

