3. BMI
4. Cardiovascular system
 - i. BP
 - ii. Pulse
 - iii. SPO2
5. Respiratory system
 - i. Respiratory rate
6. Abdominal examination
 - i. Does the participant have a visible Bandl's ring?
 - ii. Doe the participant have palpable uterine contractions?
 - iii. What is fetal heart rate?
7. Vaginal examination
 - i. Is the vulva and vagina oedematous?
 - ii. Is the caput present?
 - iii. Is the pelvis adequate?
 - iv. Have the membranes ruptured?
 - v. What is the colour of the liquor?

D. Baseline laboratory test results - Maternal

Parameter	Blood	Amniotic fluid	Urine
pH		Not Applicable	Not applicable
Blood gasses		Not Applicable	Not applicable
Lactate			

E. Study drug administration

Time	
Package number	

F. Maternal outcomes after study drug administration

Time (minutes)	Lactate in maternal blood sample	Lactate in amniotic fluid sample	Maternal arterial blood gasses	Maternal pH
0				
30				
60				
90				
120				
150				

G. Maternal outcomes at birth

1. Mode of delivery
 - i. SVD
 - ii. CS
2. For all those that delivered by CS, record the myometrial lactate here
3. What was the duration of labour?
4. Measured blood loss at birth
5. How well did the uterus contract after birth? (scale 1-10)
6. Assistant at delivery?
 - i. Midwife
 - ii. Specialist
 - iii. Medical Officer
 - iv. Intern
 - v. Student
 - vi. Others
7. Did the participant sustain any injuries in the birth canal?
 - i. Yes
 - ii. No

H. Newborn outcomes at birth

1. Record the Agar score here
 - i. At one minute
 - ii. At five minutes
2. Record the birth weight here
3. Lactate in arterial cord blood
4. Lactate in venous cord blood

Within one minute of child birth	Lactate in maternal blood sample	Lactate in amniotic fluid sample	Maternal arterial blood gasses	Maternal pH
Arterial cord blood				
Venous cord blood				

I. Monitoring of side effects and adverse events for 24 hours period after administration of study drug

(Tick all that apply)

1. Frequent urge to urinate		10. Swelling of feet or lower legs	
2. Headache (continuing)		11. Unpleasant taste	
3. Loss of appetite (continuing)		12. Increased thirst	
4. Mood or mental changes		13. Unusual tiredness or weakness	
5. Muscle pain or twitching		14. Venous irritation	
6. Nausea or vomiting		15. Cellulitis	
7. Stomach cramps		16. IV site pain	
8. Nervousness or restlessness			
9. Slow breathing			

J. Follow up outcomes

1. Perinatal outcomes on the 7th day postnatal
 - i. Alive and well
 - ii. Alive and not well
 - iii. Dead

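### Symptom side effects are recorded only after dosing on one untimed 24-hour tick list, so symptoms already present or caused by surgery cannot be told from new ones, and the symptom risk differences lose precision

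*Combined protocol and SAP*

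**What the plan says.** Safety is the second of the two specific objectives. For symptoms, the Data analysis plan says "we will compare the incidence of side effects in each arm and report risk differences". It does not restrict the count to symptoms that are new or worse after dosing.

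The symptom record is Appendix 1 section I, "Monitoring of side effects and adverse events for 24 hours period after administration of study drug". It lists 16 items, each with one tick box. There is no field for onset time, severity or status before dosing. Sections A to D of the form, completed at baseline, cover sociodemographic details, obstetric history, examination and laboratory results. They ask about none of the listed symptoms; the nearest match is respiratory rate, which bears on slow breathing.

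The Adverse events/side effects paragraph plans repeated checks: "This will be done hourly for the first six hours, six hourly for the next 18 hours", and daily after that while the woman is in hospital.

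Under Intervention/Comparator, the average wait for caesarean is about 110 minutes. Women in every arm receive intravenous fluids, antibiotics and "bladder drainage and lying in left-lateral position as they are being prepared for caesarean section".

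**The concern.** Women enter this trial after prolonged, non-progressing labour, and the Introduction itself links the condition with dehydration. Thirst, nausea or vomiting, tiredness, cramps and restlessness are plausible before any study drug is given. The same symptoms can begin after an emergency caesarean, which usually falls well inside the 24-hour window. An urge to urinate is also hard to interpret when the bladder is being drained as part of routine care.

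On the printed form, a symptom present before dosing, one that starts with the infusion and one that starts after surgery would all produce the same tick. Symptoms unrelated to the drug then add variance to each arm's incidence. At stake is how sharply the trial can estimate an excess of symptoms at each dose, and whether an arm's incidence can be read as a rate of drug side effects.

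**Working it through.** **The plan's own figures.** The Sample size section gives 224 women at 91% power for an effect size of 0.2, four groups and five measurements. The correlation between measurements is not stated. Taking it as 0.5, the noncentrality is 224 × 0.2² × 5 / (1 + 4 × 0.5) = 14.93. With 3 and 220 degrees of freedom, power is 91.1%, which agrees. Then 224 / 0.8 = 280, 280 + 192 = 472, and 472 / 4 = 118, matching "We will recruit 472 participants; 118 in each of the four arms". All of this concerns efficacy; no power or precision is stated for safety.

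**Form against schedule.** Hourly checks for six hours give 6, and six-hourly checks over the next 18 hours give 18 / 6 = 3. That is 9 scheduled checks in 24 hours. The printed form has one tick per symptom for all of them, and no place for the later daily checks.

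**Effect on precision.** From the plan: n = 118 per arm, one active arm against placebo. Assumed, because the documents give no symptom rates: a share q of women has the symptom before dosing, and among the others it newly appears in a proportion a on placebo and c on active drug.

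- As planned (any tick): p0 = q + (1 − q)a, p1 = q + (1 − q)c.
- New symptoms only, all randomised women as denominator: p0 = (1 − q)a, p1 = (1 − q)c.
- In both cases the difference is (1 − q)(c − a), SE = √[p0(1 − p0)/118 + p1(1 − p1)/118], the 95% half-width is 1.96 × SE, and z is the difference divided by SE.

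Worked case with q = 30%, a = 5%, c = 15%:

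- As planned: 33.5% against 40.5%; SE = √[0.335 × 0.665/118 + 0.405 × 0.595/118] = 0.0627; z = 0.07/0.0627 = 1.12.
- New only: 3.5% against 10.5%; SE = √[0.035 × 0.965/118 + 0.105 × 0.895/118] = 0.0329; z = 0.07/0.0329 = 2.13.

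All cases with a = 5%, c = 15%:

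| Pre-existing q | Difference (points) | Half-width as planned | Half-width new only | z as planned | z new only |
|---|---|---|---|---|---|
| 0% | 10.0 | 7.5 | 7.5 | 2.60 | 2.60 |
| 10% | 9.0 | 9.9 | 7.2 | 1.77 | 2.45 |
| 30% | 7.0 | 12.3 | 6.4 | 1.12 | 2.13 |
| 50% | 5.0 | 12.7 | 5.5 | 0.77 | 1.77 |

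**When onset after surgery is common.** Take q = 30%, a = 40%, c = 50%. As planned the rates are 58% and 65%, half-width 12.4, z = 1.11. Counting new symptoms only, they are 28% and 35%, half-width 11.8, z = 1.16. A pre-dose checklist then gains almost nothing, because most of the noise arises after dosing.

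The model counts only new onset; worsening of a symptom already present is not included.

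**The case against.** The strongest case on the other side has five parts.

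- **No background rate is documented.** A reader might infer that the recorded incidence will be mostly background. The documents give no rate for any symptom, and at 0% pre-existing nothing is lost. This objection stands, so the result is shown as a range.
- **The comparison is not made unfair.** A reader might infer a bias towards no difference that the fix would remove. Allocation is random and the control is placebo, so background is balanced in expectation. With all randomised women as denominator, the risk difference is the same under both counts (7.0 points at 30%); only the interval narrows. Nor does the Data analysis plan base a formal claim of safety on a non-significant result: it states no equivalence or non-inferiority test. This stands.
- **Safety does not rest on the checklist alone.** A reader might infer that the whole safety objective is weakened. Electrolytes, blood gases, pH and bicarbonate are measured at baseline and serially (Table 1). Postpartum haemorrhage, sepsis and death are separate outcomes, and serious adverse events are monitored. None of these is affected. Infusion-site items and unpleasant taste are also less likely to be present before dosing. This stands.
- **Much of the background may come from surgery.** The 110-minute wait is 110/1440 = 7.6% of the window, and the Sample size section notes that many women deliver within 30 minutes of baseline. This stands, and it means that a pre-dose tick alone is not enough.
- **Handling may be better than the printed form shows.** Some items are worded as a change or as persisting (thirst, tiredness, headache, appetite), and the questionnaire is electronic, so entries may be repeated or time-stamped. This stands in part: the documents do not establish that every pre-existing symptom would be ticked. They also give no rule for such symptoms, and a change is hard to judge without a recorded starting point.

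**Conclusion.** The point holds as a gap in data capture and endpoint definition. Pre-dose status, onset time and severity are not specified for the symptom checklist, the printed form cannot hold the scheduled checks, and raw incidence is analysed. The cost is lost precision in the symptom risk differences, and arm-level incidences that cannot be read as drug side effects.

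The size depends on assumed rates. It ranges from no loss when no woman has the symptom beforehand to roughly a halving of z (2.13 to 1.12) at 30% pre-existing with little other new onset. Where new onset after surgery is frequent, the pre-dose checklist alone recovers almost none of the precision, and onset time relative to birth is needed to interpret the ticks. The benefit of that split has not been quantified.

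This is an inexpensive improvement worth making, and it does not call the validity of the trial into question. It should be made before recruitment proceeds, since pre-dose status cannot be reliably recovered afterwards.

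**What to change.** 1. **Pre-dose checklist.** The research midwife completes the section I items once in the baseline questionnaire, before the study package is opened.
2. **Timed grid.** Replace the single tick list with a grid at the checks already scheduled in the Adverse events/side effects paragraph, including the daily ones. Record onset time, severity, and whether each symptom is new, worse or unchanged from before dosing.
3. **Endpoint definition.** In the Data analysis plan, define the symptom safety outcome as new or worse after dosing, with all randomised women as denominator. Report risk differences against placebo overall and by onset before or after birth. Keep the overall figure as the main one, because time of birth is itself a post-randomisation event.

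**Cost.** A short extra questionnaire before dosing in an emergency setting, and a longer form at checks already planned. No additional samples or visits are needed. The documents give no basis for the time per woman, so the training dry run should measure it.
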